11.2 Database management and quality control

Novartis personnel (or designated CRO) will review the data entered by investigational staff for completeness and accuracy. Electronic data queries stating the nature of the problem and requesting clarification will be created for discrepancies and missing values and sent to the investigational site via the EDC system. Designated investigator site staff are required to respond promptly to queries and to make any necessary changes to the data.

Concomitant treatments and prior medications entered into the database will be coded using the WHO Drug Reference List, which employs the Anatomical Therapeutic Chemical classification system. Medical history/current medical conditions and adverse events will be coded using the Medical dictionary for regulatory activities (MedDRA) terminology.

Randomization codes and data about all study treatment(s) dispensed to the subject will be tracked using an Interactive Response Technology (IRT). The system will be supplied by a vendor, who will also manage the database. The data will be sent electronically to Novartis (or a designated CRO) at specific timelines.

Each occurrence of a code break via IRT will be reported to the clinical team and monitor. The code break functionality will remain available until study shut down or upon request of Novartis.

Once all the necessary actions have been completed and the database has been declared to be complete and accurate, it will be locked **and the treatment codes will be unblinded** and made available for data analysis/moved to restricted area to be accessed by independent programmer and statistician. Any changes to the database after that time can only be made after written agreement by Novartis development management.

11.3 Site monitoring

Before study initiation, at a site initiation visit or at an investigator's meeting, a Novartis/delegated CRO representative will review the protocol and data capture requirements (i.e. eCRFs) with the investigators and their staff. During the study, Novartis employs several methods of ensuring protocol and GCP compliance and the quality/integrity of the sites' data. The field monitor will visit the site to check the completeness of subject records, the accuracy of data capture / data entry, the adherence to the protocol and to Good Clinical Practice, the progress of enrollment, and to ensure that study treatment is being distributed and accounted for according to specifications. Key study personnel must be available to assist the field monitor during these visits. Continuous remote monitoring of each site's data may be performed by a centralized Novartis/delegated CRO/CRA organization. Additionally, a central analytics organization may analyze data & identify risks & trends for site operational parameters, and provide reports to Novartis clinical teams to assist with trial oversight.

The investigator must maintain source documents for each subject in the study, consisting of case and visit notes (hospital or clinic medical records) containing demographic and medical information, laboratory data, electrocardiograms, and the results of any other tests or assessments. All information on CRFs must be traceable to these source documents in the subject's file. The investigator must also keep the original informed consent form signed by the subject (a signed copy is given to the subject).

The investigator must give the monitor access to all relevant source documents to confirm their consistency with the data capture and/or data entry. Novartis monitoring standards require full verification for the presence of informed consent, adherence to the inclusion/exclusion criteria, documentation of SAEs, and of data that will be used for all primary variables. Additional checks of the consistency of the source data with the CRFs are performed according to the study-specific monitoring plan. No information in source documents about the identity of the subjects will be disclosed.

12 Data analysis and statistical methods

Any data analysis carried out independently by the investigator should be submitted to Novartis before publication or presentation.

12.1 Analysis sets

The Full Analysis Set (FAS) population will serve as the primary population for the analysis of efficacy data in this trial.

The FAS comprises all subjects to whom study treatment has been assigned by randomization and who have a baseline observation and at least one post-randomization observation for the analysis endpoint. According to the intent-to-treat principle, subjects will be analyzed according to the treatment they have been assigned to during the randomization procedure.

The Safety Set includes all randomized subjects who received the study treatment, with subjects included in the treatment group corresponding to the treatment they actually received.

While no per-protocol analysis is planned, a list of protocol violators (e.g. subjects with lack of study treatment compliance, change in background therapy during the trial) will be finalized prior to unblinding.

12.2 Subject demographics and other baseline characteristics

Demographic and other baseline data will be listed and summarized descriptively by treatment group for the FAS and the Safety Set.

Categorical data will be presented as frequencies and percentages. For continuous data, mean, standard deviation, median, minimum, and maximum will be presented.

Relevant medical histories and current medical conditions at baseline will be summarized by system organ class and preferred term, by treatment group.

12.3 Treatments

The Safety Set will be used for the analyses below. Categorical data will be summarized as frequencies and percentages. For continuous data, mean, standard deviation, median, 25th and 75th percentiles, minimum, and maximum will be presented.

The duration of exposure to the study treatment will be summarized using descriptive statistics.

Concomitant medications and significant non-drug therapies prior to and after the start of the study treatment will be listed and summarized according to the Anatomical Therapeutic Chemical (ATC) classification system, by treatment group.

Reasons for discontinuation for all patients will be listed and tabulated for both treatment groups. The median time to all-cause discontinuation will be compared between the treatment groups. The log-rank test will be used to test the null hypothesis against the alternate hypothesis that the median time to discontinuation is not the same between the groups.

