Mis-randomized subjects	Mis-randomized subjects are those who were not qualified for randomization and who did not take study treatment, but have been inadvertently randomized into the study
Other treatment	Treatment that may be needed/allowed during the conduct of the study (concomitant or rescue therapy)
Part	A sub-division of a study used to evaluate specific objectives or contain different populations. For example, one study could contain a single dose part and a multiple dose part, or a part in subjects with established disease and in those with newly-diagnosed disease.
Patient	An individual with the condition of interest for the study
Period	The subdivisions of the trial design (e.g. Screening, Treatment, Follow-up) which are described in the Protocol. Periods define the study phases and will be used in clinical trial database setup and eventually in analysis
Personal data	Subject information collected by the Investigator that is transferred to Novartis for the purpose of the clinical trial. This data includes subject identifier information, study information and biological samples.
Premature subject withdrawal	Point/time when the subject exits from the study prior to the planned completion of all study treatment administration and/or assessments; at this time all study treatment administration is discontinued and no further assessments are planned
Randomization number	A unique identifier assigned to each randomized subject
Screen Failure	A subject who did not meet one or more criteria that were required for participation in the study

Source Data/Document	Source data refers to the initial record, document, or primary location from where data comes. The data source can be a database, a dataset, a spreadsheet or even hard-coded data, such as paper or eSource.
Start of the clinical trial	The start of the clinical trial is defined as the signature of the informed consent by the first subject.
Study treatment	Any single drug or combination of drugs or intervention administered to the subject as part of the required study procedures.
Study treatment discontinuation	When the subject permanently stops taking any of the study treatments prior to the defined study treatment completion date (if any) for any reason; may or may not also be the point/time of study discontinuation
Subject	A trial participant (can be a healthy volunteer or a patient)

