Subject number	A unique number assigned to each subject upon signing the informed consent. This number is the definitive, unique identifier for the subject and should be used to identify the subject throughout the study for all data collected, sample labels, etc.
Treatment arm/group	A treatment arm/group defines the dose and regimen or the combination, and may consist of 1 or more cohorts.
Variable	A measured value or assessed response that is determined from specific assessments and used in data analysis to evaluate the treatment being tested in the study
Withdrawal of study consent	Withdrawal of consent from the study occurs only when a subject does not want to participate in the study any longer, and does not allow any further collection of personal data.

Corporate Confidential Information

Protocol summary

Protocol number	CPEA001A12201
Full Title	A Randomized, Sham-Controlled Study of PEAR-004 as an adjunct to standard-of-care treatment for schizophrenia
Brief title	Study of efficacy of PEAR-004 in schizophrenia
Sponsor and Clinical Phase	Novartis Phase II
Investigation type	Device
Study type	Interventional
Purpose and rationale	
The purpose of the study is to determine in patients currently being administered antipsychotic pharmacotherapy whether PEAR-004 can further reduce symptoms of schizophrenia as measured by the Positive and Negative Syndrome Scale (PANSS).
 
The overall rationale for the study is to assess the first prescription digital therapeutic (PDT) in schizophrenia using a form of proven psychosocial intervention, cognitive behavioral therapy (CBT), to supplement standard of care with antipsychotic medications.

Primary Objective(s)	The primary objectives are to assess the efficacy of PEAR-004 as an adjunct to existing clinician-directed pharmacotherapy to reduce symptoms of schizophrenia by change in total PANSS score, and to evaluate retention to assigned study treatment by percent dropout rate at the end of the study

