Data analysis	
The change from baseline in total PANSS score will be analyzed using the mixed-effects model for repeated measures (MMRM), with fixed, categorical effects of treatment, visit, and treatment-by-visit interaction, as well as the continuous, fixed covariates of baseline score, baseline score-by-visit interaction, and disease duration at baseline. An unstructured covariance structure will be used to model the within-patient errors. The Kenward-Roger method will be used to adjust the estimated covariance of the mean difference and the degrees of freedom. Several other covariance structures will be tested if there are convergence issues in the primary analysis.
 
The primary hypothesis to be tested is that mean change from baseline in PANSS is greater with PEAR-004 than with Sham at day 85 or last visit. The primary comparison will be the contrast between treatments on day 85. The significance test will be carried out using 1-sided $\alpha=0.05$. In addition, two-sided 90% confidence intervals for the treatment mean differences, as well as individual treatment mean change from baseline values at each study visit will be constructed.
 
Two sensitivity analyses (the selection model and the pattern mixture model) will be performed to assess the robustness of the primary analysis to missing data results. The LOCF approach will also be performed to aid in the interpretation of the results from the primary analysis.

Key words	Schizophrenia, prescription digital therapeutic, cognitive behavioral therapy, smartphone app

1 Introduction

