1.2 Purpose

The purpose of the study is to determine in patients currently being administered antipsychotic pharmacotherapy whether PEAR-004 can further reduce symptoms of schizophrenia as measured by the total score on the Positive and Negative Syndrome Scale (PANSS).

2 Objectives and endpoints

Table 2-1 Objectives and related endpoints

Objectives and endpoints	
Primary Objective	
Objective	Endpoint

 To assess the efficacy of PEAR-004 as an adjunct to existing clinician-directed pharmacotherapy to reduce symptoms of schizophrenia 	
 Change in total PANSS score from baseline to day 85 or last visit

 To evaluate retention to assigned study treatment 	
 Percent dropout rate
Secondary Objectives	
Objectives	Endpoints

 To evaluate the efficacy of PEAR-004 as an adjunct to existing clinician-directed pharmacotherapy to reduce positive symptoms of schizophrenia 	
 Change in the Positive PANSS score from baseline to day 29, day 57, and day 85 or last visit Change in the General Psychopathology PANSS score from baseline to day 29, day 57 and day 85 or last visit

 To evaluate the efficacy of PEAR-004 as an adjunct to existing clinician-directed pharmacotherapy to reduce negative symptoms of schizophrenia 	
 Change in the Negative PANSS score from baseline to day 29, day 57, and day 85 or last visit Change in the Motivation and Pleasure self-report (MAP-SR) score from baseline to day 29, day 57, and day 85 or last visit

 To assess safety and tolerability of PEAR-004 	
 Adverse events, serious adverse events, and adverse events leading to discontinuation throughout the study

	
 • Vital signs at baseline, day 85 or last visit • InterSePT Scale for Suicidal Thinking-Plus (ISST-Plus) score at baseline, day 29, day 57, day 85, and day 115 or last visit

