Subjects in both groups will continue to receive their clinician-directed standard of care treatment for schizophrenia, including pharmacotherapy. Subjects in Group A will use PEAR-004 for a period of 12 weeks. Subjects in Group B will use a sham for a period of 12 weeks. Subjects will return to the clinic for outpatient visits at week 4 (day 29), week 8 (day 57), and week 12 (day 85). At each visit, standard assessments will be performed according to the assessment schedule, including PANSS, ISST-Plus, CGI, BMQ, MAP-SR, WHOQOL-BREF, BDI-II, ISI, and Adverse Events (AEs). A final follow-up visit will be performed at week 16 (day 115), including the assessments as detailed in the assessment schedule.

Figure 3-1 Study Design

4 Rationale

The overall rationale for the study is to assess the first PDT in schizophrenia using evidence-based coping skills to supplement standard of care with antipsychotic medications.

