9.1.3 Lost to follow-up

For subjects whose status is unclear because they fail to appear for study visits without stating an intention to discontinue or withdraw, the investigator must show "due diligence" by documenting in the source documents steps taken to contact the subject, e.g. dates of telephone calls, registered letters, etc. A subject should not be considered as lost to follow-up until due diligence has been completed or until the end of the study.

In order to better adhere to the intent-to-treat principle, subjects will be encouraged to continue in the trial even if they discontinue treatment (often referred to as "retrieved dropout").

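### Percent dropout is a listed primary endpoint, but the only visible between-arm comparison is of median time to discontinuation, as treated, with a log-rank test worded as a test of medians

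*Protocol*

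**What the plan says.** The Primary Objective(s) row of the Protocol summary includes the aim "to evaluate retention to assigned study treatment by percent dropout rate at the end of the study". Protocol Table 2-1 and SAP 1.3.1 give the matching primary endpoint as "Percent dropout rate".

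The sections that define the primary analysis (Protocol 12.4.1, SAP 6.1) cover total PANSS change only. The Data analysis row of the Protocol summary, which shows no redaction mark, also states a hypothesis for PANSS only: "The primary hypothesis to be tested is that mean change from baseline in PANSS is greater with PEAR-004 than with Sham".

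Discontinuation is handled under Treatments in Protocol 12.3 and SAP 7.2:
- Reasons for stopping are listed and tabulated by group. Categorical data in that section are given as counts and percentages.
- "The median time to all-cause discontinuation will be compared between the treatment groups".
- A log-rank test is specified, with the alternative that the two medians differ.
- All of this uses the Safety Set, which Protocol 12.1 and SAP 4 define as randomized subjects who received study treatment, "with subjects included in the treatment group corresponding to the treatment they actually received".

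The Protocol glossary defines study treatment discontinuation as a permanent stop "prior to the defined study treatment completion date (if any) for any reason". Treatment lasts 12 weeks in both arms; for the active arm, Protocol 3 says "Subjects in Group A will use PEAR-004 for a period of 12 weeks". Protocol 9.1.3 separates stopping treatment from leaving the study: "subjects will be encouraged to continue in the trial even if they discontinue treatment".

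**The concern.** The endpoint is a percentage on the assigned treatment. The planned comparison is of a median time, in subjects grouped by treatment received. These differ in three ways.

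1. A Kaplan-Meier median exists only if the curve falls to 50%. Over 12 weeks with about 51 per arm, that needs roughly half of an arm to stop.
2. The log-rank test compares whole discontinuation-time distributions. A significant result reported in the plan's words would claim a difference in medians that the data need not show.
3. Neither a median nor a log-rank p-value says by how many percentage points the arms differ in dropout, or how precisely that difference is known.

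At stake is the interpretation of one listed primary endpoint.

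**Working it through.** **Inputs.** 102 subjects randomized 1:1, so 51 per arm (Protocol 12.8.1). Treatment lasts 12 weeks, 84 days (Protocol 3). The documents give no expected dropout, so every dropout rate below is an assumption.

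**The plan's own figures.** Sizing is for PANSS only. Power = Φ(Δ / (SD·√(2/51)) − 1.645). For Δ = 8 and SD = 16: 8 / 3.169 = 2.525; 2.525 − 1.645 = 0.880; Φ(0.880) = 81.1%. For Δ = 4, 6, 8 and 10 the normal formula gives 35.1%, 59.8%, 81.1% and 93.5%, and the noncentral t gives 34.8%, 59.3%, 80.6% and 93.2%. Table 12-1 states 35%, 59%, 81% and 93%. It reproduces, and nothing in it concerns dropout.

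**Can the median be estimated?** Without censoring before the end of treatment, an arm reaches its median if at least 26 of 51 stop. Let q = P(X ≥ 26 | n = 51, p). The chance that neither arm reaches it, with the same p in both, is (1 − q)².

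| True dropout p | q, one arm | Neither arm |
|---|---|---|
| 30% | 0.14% | 99.7% |
| 35% | 1.4% | 97.3% |
| 40% | 7.4% | 85.8% |
| 45% | 23.6% | 58.4% |
| 50% | 50.0% | 25.0% |
| 60% | 92.6% | 0.5% |

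Censoring during treatment can bring the curve to 50% with fewer than half stopping, but it changes little. With 10% or 20% independent censoring, q is 0.17% or 0.30% at p = 30%, 8.0% or 8.7% at 40%, and 24% or 25% at 45% (100,000 simulated arms).

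**What does the log-rank test respond to?** Simulation used 51 per arm, administrative censoring at 84 days, two-sided 5% and 20,000 runs.
- 30% vs 30% dropout: rejects in about 5%, so size is correct.
- 10% vs 30%: rejects in about 73%, with neither median reached in 99.9%.
- 20% vs 40%: rejects in about 61%, with neither median reached in about 93%.
- Equal true medians of 120 days, exponential against Weibull with shape 2: rejects in about 24%. True dropout by the end of treatment is then 38% against 29%.

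The test therefore works without estimable medians, and rejection does not show that medians differ.

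**What would a risk difference give?** The Newcombe interval uses the Wilson limits (l, u) of each arm: lower = d − √((p₁ − l₁)² + (u₂ − p₂)²), upper = d + √((u₁ − p₁)² + (p₂ − l₂)²).
- 15/51 vs 10/51: d = 29.4% − 19.6% = 9.8 points. The 90% Wilson limits are 20.2% to 40.7% and 12.1% to 30.2%, giving −4.2 to 23.4. The 95% interval is −6.9 to 25.9.
- 20/51 vs 10/51: d = 19.6 points, 90% interval 4.8 to 33.4, 95% interval 1.9 to 35.8.

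It can be estimated at any dropout rate.

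**Analysis set.** Leaving out one never-starter who would count as a dropout moves an arm from 10/51 = 19.6% to 9/50 = 18.0%, or from 20/51 = 39.2% to 19/50 = 38.0%. That is about 1.2 to 1.6 points each.

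**The case against.** The strongest reply is that the objective is only to evaluate retention. No superiority hypothesis on dropout is stated, and the trial is sized for PANSS alone. Protocol 12.3 tabulates discontinuation with percentages, so the listed endpoint will appear per arm and the difference is a subtraction. The log-rank test is valid, and under proportional hazards equal medians and equal distributions coincide. In the equal-medians example the arms truly differ in dropout (38% vs 29%), so rejecting is the right answer for retention.

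Most of this stands, and it rules out several stronger readings that a reader might infer:
- **That dropout will go unreported.** It will not; what is missing is a between-arm difference with an interval.
- **That the log-rank test is wrong.** Only the reference to medians is.
- **That the medians will certainly not be reached.** The documents give no dropout rate, and at 60% per arm they usually would be.
- **That dropout needs a new definition.** The objective's reference to the assigned treatment, with the glossary and Protocol 9.1.3, points to treatment discontinuation. On that reading the event falls within the 12 weeks, so day 85 and day 115 give the same percentage. The day matters only if study withdrawal is meant.
- **That no dropout analysis exists anywhere.** Text is withheld in Protocol 12.4.2, 12.4.4.1 and 12.5.1, and in SAP 2, 6.1.2, 6.1.2.1 and 6.2.3, so this cannot be shown. The summary's Data analysis row makes a gap plausible but does not prove it.

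The reply does not answer why a listed primary endpoint should be compared through a summary that may not exist, in an as-treated set, under a hypothesis that the test does not address.

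**Conclusion.** The point holds as a minor one. In the visible text, the between-arm comparison for a listed primary endpoint targets median time rather than percent dropout, groups subjects by treatment received although the objective concerns assignment, and misstates the log-rank alternative.

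The median is likely to be uninformative if dropout is about 40% or less per arm, with an 86% or greater chance that neither arm reaches it. That chance falls quickly above 40%. These figures assume 51 per arm, equal dropout in both arms and no censoring before the end of treatment.

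The analysis-set mismatch is probably small. Site staff are trained to install the assigned app through an access code (Protocol 6.1), which makes crossovers and never-starters less likely. A reader might infer a multiplicity problem from two primary endpoints; that is not claimed here, because the visible text sets a formal primary hypothesis for PANSS only.

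**What to change.** Amend the SAP before database lock. Where the wording of Protocol 12.3 changes, Protocol 14.1 requires a written protocol amendment with the approvals listed there.

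1. Report percent dropout per arm and the risk difference with a score-based interval (for example Newcombe), in all randomized subjects by assigned arm, and state how never-starters count. Add the Kaplan-Meier percent discontinued at the end of treatment.
2. State the interval level and match it to the sidedness of the test: 90% for one-sided 5%, 95% for two-sided 5%. The choice must be explicit. The Protocol summary pairs 90% intervals with a one-sided PANSS test, SAP 6.1.2.2 and 6.2.2 use 95%, and the log-rank alternative is worded two-sided.
3. Drop the median as the between-arm summary and restate the log-rank null as equal discontinuation-time distributions.
4. Cross-refer dropout to the glossary term for study treatment discontinuation.

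The cost is one extra table and a short amendment. No new data are needed.
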